MIB requires a considerable amount of physician technical expertise and the majority of radiation oncologists who treat breast cancer routinely do not have training to perform these procedures. The MammoSite® (Hologic Inc., Marlborough, MA) breast brachytherapy applicator was designed to treat a similar volume of tissue around the lumpectomy cavity as MIB but with a single skin entry point, greater simplicity and less user-dependence.¹⁹ The American Society of Breast Surgeons (ASBS) MammoSite Breast Brachytherapy Registry Trial reported the outcomes of 1440 patients treated with this technique between 2002 and 2004 at 97 institutions. With a median follow-up for surviving patients of 53.7 months, the 5-year actuarial rate of ipsilateral breast tumor recurrence (IBTR) was 3.8% (3.86% for the 1249 patients with invasive breast cancer, 3.39% for the 194 patients with DCIS). In patients with invasive breast cancer, the 5-year actuarial rate of regional nodal failure was 0.84%. Negative estrogen receptor status was the only variable significantly associated with ipsilateral breast tumor recurrence (IBTR) and was limited to the development of breast failures several centimeters from the primary site and believed to be a new primary cancer. 90.6% of patients had a good or excellent cosmetic result at 5 years, and the only factor significantly associated with favorable cosmesis was increasing balloon-to-skin distance.²⁰

Multi-lumen balloon catheter devices (Mammosite® ML and Contura® [SenoRx, Irvine, CA]) and non-balloon bundled-catheter device (SAVI® [Strut Adjusted Volume Implant], Cianna Medical, Aliso, Viejo, CA]) were developed to provide greater conformality to the lumpectomy cavity while enabling better tailoring of dose around normal tissue structures like the skin, chest wall, and heart compared with single-lumen applicators. Fisher et al. reported their results of treatment of 117 patients with APBI brachytherapy between 2004 and 2010.²¹ Seventy-seven were treated with single-lumen balloon catheter Mammosite® and 40 with the SAVI® applicator, all to total doses of 34Gy in 10 fractions. Of the 40 patients treated with the SAVI® device, 12 had tumor bed-to-skin spacing of less than 7mm. None of these patients required device explantation, compared to 57% of patients treated with Mammosite when distances were <7mm. All 12 SAVI patients with minimal skin spacing had good or excellent cosmesis at short interval follow-up of 13 months thus far.²¹

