6.0 Randomization/Registration Procedures

6.1 Randomization-none

6.2 Registration Procedures

Registration will entail confirming patient eligibility and signing the informed consent

6.21 Pretreatment tests/procedures, (see Section 4.0) will be completed within the guidelines specified on the assessment schedule.

6.22 All required baseline symptoms (see Section 10.0) must be documented and graded.

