As the implanted device moves with the target, compensation for variability of treatment set-up and breathing motion is not needed; therefore planning target volume for evaluation (PTV_EVAL) = CTV = PTV. Therefore, within this protocol, only the PTV_EVAL will be referenced. The PTV_EVAL will be delineated as the breast tissue volume bounded by the uniform expansion of the applicator surface radius in all dimensions by 10 mm less the applicator volume and will be limited to 5 mm from the skin surface and by the posterior breast tissue extent (chest wall and pectoralis muscles are not to be included).

The volume of trapped air/fluid that displaces the target beyond 1 cm from the balloon/applicator surface should be considered by the physician. The area of trapped air/fluid will be contoured at each level and a total volume obtained. The percentage of the PTV_EVAL that the air displaces may be calculated but this will not be considered in the PTV prescription constraints outlined below. If brachytherapy APBI is attempted but aborted prior to initiation because target coverage or normal tissue constraints (see below) cannot be met, then an alternative APBI technique (3DCRT photon or proton APBI) may be attempted on this protocol.

Dose Prescription to PTV_Eval: The prescribed radiotherapy dose will be 21 Gy in 7 Gy daily fractions (total of 3 fractions). Radiotherapy should aim to be delivered on three consecutive work days. Per protocol $\geq 95\%$ of the target volume PTV should be covered by $\geq 95\%$ of the prescribed dose of 21 Gy. High dose rate treatment delivery is required. Variation Acceptable $\geq 90\%$ of the target volume PTV should be covered by $\geq 90\%$ of the prescribed dose of 21 Gy. The volume receiving 150% and 200% (V150% and V200%) of the prescribed dose or more should be $\leq 35\text{cc}$ and $\leq 10\text{cc}$, respectively. Variation Acceptable V150%

<50cc and V200% <15cc. The volume receiving 300% and 400% (V300% and V400%) of the prescribed dose should be reported.

Definition and Dose Limitations of Normal Tissues/Organs at Risk (OARs): The following normal tissue structures should be contoured for all patients: uninvolved normal breast, ipsilateral lung, contralateral lung, heart, skin, adjacent ribs.

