8.2 Radiation Therapy Adverse Events

The descriptions and grading scales found in the revised NCI Common Terminology Criteria for Adverse Events (CTCAE), version 4 will be utilized for grading all adverse events. All appropriate treatment areas should have access to a copy of the CTCAE, v. 4. A copy of the CTCAE, v. 4 can be downloaded from the CTEP web site
 (██████████).

EVENTS EXPECTED

Erythema, dry desquamation, hyper or hypopigmentation are anticipated to occur commonly. Some patients may develop moist desquamation, which usually heals within 2-3 weeks. Mild swelling of the breast or mild breast pain are also likely side effects of treatment. It is not anticipated that treatment breaks should be needed, as severe acute toxicities are extremely rare.

Transient, persistent, and occasionally symptomatic seroma formation can occur and will be monitored for during treatment and at follow-up. Telangiectasia, and chronic changes in pigmentation can also commonly be seen, as can soft tissue fibrosis.

Infection is less likely, occurring in less than 10% of patients, generally following brachytherapy.

Skin or subcutaneous toxicity requiring surgery, pneumonitis, rib fractures, or any grade 3 or greater complications including pain are uncommon after ABPI, and are expected to occur in <10% of patients

Patients will also undergo venipuncture as part of the study. Risks of that procedure include hematoma, swelling, tenderness and inflammation at the site, persistent bleeding, vasovagal response, and rarely thrombosis and infection.

Method of detection, signs and symptoms, and method of treatment will be reported for all detected toxicities

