16.3 **Secondary Endpoints:** The secondary aims of this study are to characterize acute and late adverse events, assess patient self-reported and panel-reported cosmesis, IBTR rate, and quality of life as well as exploratory comparisons of cosmesis, toxicity, and IBTR rate between the 3 techniques. In addition, regional recurrence rates, distant recurrence rates, invasive disease-free survival, and overall survival will be estimated for each patient group treated with APBI. Blood will be collected for future studies in order to examine molecular and genomic predictors of adverse cosmesis and late toxicity.

The following definitions are used for the secondary endpoints of interest:

- *Acute adverse events* (up to 1 month post-RT): any adverse event, regardless of attribution, that occurs in the first month post-RT.
- *Late adverse events* (up to 3 years post XRT): any adverse event that occurred after the first month post-RT and up to 3 years post-RT.
- *Patient Reported Outcomes/Quality of life:* the Patient-Reported Outcomes Version of the Common Terminology Criteria for Adverse Events (PRO-CTCAE) will be used for patient self-reporting of toxicities in the CTCAE, along with other measures of fatigue, pain, and arm function listed in the appendix.
- *Patient self-reported cosmetic outcomes:* the patient self-reported outcome will be assessed using a modified Harvard Cosmesis Scale in the Breast Cancer Treatment Outcome Scale (BCTOS).
- *Panel assessed cosmetic outcome:* in addition to patient self-reported and physician reported outcomes, cosmesis will be assessed by a panel of breast cancer medical providers using digital photographs. The Panel will be blinded to treatment allocation.
- *IBTR:* this is defined as local recurrence at 3 years from trial registration as a first event. IBTR is defined as both invasive and non-invasive breast cancer involving the same breast parenchyma as the original tumor.
- *Regional recurrence:* invasive breast cancer in the axilla, regional lymph nodes, chest wall, and skin of the ipsilateral breast.
- *Distant recurrence:* metastatic cancer that has either been biopsy confirmed or clinically diagnosed as recurrent invasive breast cancer.

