16.61 *Acute adverse events (up to 90 days post-RT):* All patients who were registered to the study and started treatment will be included in the acute adverse event analysis. An acute adverse event is an AE, regardless of attribution, that occurs up to 90 days post-RT. The maximum grade for each type of acute AE will be recorded for each patient. Data will be summarized as frequencies and relative frequencies. Additionally, the relationship of the adverse event(s) to the study treatment will be taken into consideration.

16.62 *Late adverse events:* All patients who were registered to the study and started treatment will be included in the late adverse event analysis. A late adverse event is an AE, regardless of attribution, that occurs at least 90 days post-RT and up to 3 years post-RT. The maximum grade for each type of late AE will be recorded for each patient. Data will be summarized as frequencies and relative frequencies. Additionally, the relationship of the adverse event(s) to the study treatment will be taken into consideration. Prior APBI reports have suggested rates of grade 3 or 4 toxicity to be $\leq 10\%$.^{18,47,55,56}

16.63 *Quality of life:* The QOL measurements will be summarized at each time point as mean \pm SD and median (minimum value, maximum value). Changes in the QOL measurements from baseline will be determined at each follow-up measurement. These will be displayed as spaghetti plots. The assessment of the changes at each time point will be done with a paired t-test or Wilcoxon signed rank test, whichever is appropriate.

16.64 *Cosmesis*: The values of the cosmesis instruments (patient self-reported and panel-assessed) will be summarized with the frequencies of fair or poor cosmesis events at baseline and 3 years, and the difference at 3 years, as well as their relative exact binomial confidence intervals.

16.65 *IBTR incidence*: The IBTR cumulative incidence will be estimated using a competing risks method (Gooley et al.). The competing risks will be regional/distant breast cancer recurrence and death.

16.66 *Regional recurrence incidence*: The regional breast cancer recurrence cumulative incidence will be estimated using a competing risks method (Gooley et al.). The competing risks will be local/distant breast cancer recurrence and death.

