16.9 Data & Safety Monitoring

16.91 The principal investigator(s) and the study statistician will review the study at least every quarter to identify accrual, adverse events, and any endpoint problems that might be developing. The Mayo Clinic Cancer Center (MCCC) Data Safety Monitoring Board (DSMB) is responsible for reviewing accrual and safety data for this trial at least twice a year, based on reports provided by the MCCC Statistical Office.

16.92 Adverse Event Stopping Rules: The stopping rules specified below are based on knowledge available at study development. We note that the Adverse Event Stopping Rule may be adjusted in the event of either (1) the study re-opening to accrual or (2) at any time during the conduct of the trial and in consideration of newly acquired information regarding the adverse event profile of the treatment(s) under investigation. The study team may choose to suspend accrual because of unexpected adverse event profiles that have not crossed the specified rule below. The following rule will be evaluated for each arm separately.

Accrual will be temporarily suspended if at any time we observe events considered at least possibly related to study treatment (i.e. an adverse event with attribute specified as “possible,” “probable,” or “definite”) that satisfy one of the following:

- If 3 or more patients in the first 15 treated patients experience a grade 3 or higher adverse event, besides acute dermatitis, that is at least possibly related to treatment within 90 days post treatment..
- After the first 15 patients have been treated: if $\geq 20\%$ of all patients experience a grade 3 or higher adverse event, besides acute dermatitis, that is at least possibly related to treatment within 90 days post treatment.

Similarly, within each of the modalities (photon, proton, or brachytherapy APBI), accrual will be suspended for that modality:

- If 6 or more patients in the first 30 treated patients experience a grade 3 or higher adverse event at least possibly related to treatment at any time after 6 months following completion of the protocol treatment.
- After the first 30 patients have been treated: if $\geq 20\%$ of all patients experience a grade 3 or higher adverse event at least possibly related to

treatment at any time after 6 months following the completion of protocol treatment.

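### A woman implanted for brachytherapy who never receives a fraction appears to fall outside the AE rates and the per-arm suspension count, and no rule says which technique holds her device events

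*Combined protocol and SAP*

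**What the plan says.** **Safety sets.** Section 16.61: "All patients who were registered to the study and started treatment will be included in the acute adverse event analysis". Section 16.62 uses the same set for late events. The acute suspension rule in 16.92, evaluated for each arm, reads in part: "If 3 or more patients in the first 15 treated patients experience a grade 3 or higher adverse event, besides acute dermatitis". The event must also be at least possibly related to treatment and fall within 90 days post treatment. No section defines what starts treatment.

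**Device timing.** Under 7.12 consent may be taken before surgery. The catheter is placed in the same operation as the lumpectomy, planning follows on days 2 to 4, and brachytherapy generally starts one to five days after placement. Antibiotic cover runs from before placement until the device is out.

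**Stopping before the first fraction.** Section 7.12 foresees this: "If brachytherapy APBI is attempted but aborted prior to initiation because target coverage or normal tissue constraints (see below) cannot be met". The patient may then have photon or proton APBI on study. The brachytherapy skin constraint in 7.12 opens a similar route. Neither says which technique holds the patient, or events that have already occurred.

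**Windows.** In 16.61: "An acute adverse event is an AE, regardless of attribution, that occurs up to 90 days post-RT". In 16.3 the acute event is instead "any adverse event, regardless of attribution, that occurs in the first month post-RT".

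**Baseline.** Footnote 2 of the test schedule (4.0) asks only that baseline procedures precede radiation. Registration (6.2): "Registration will entail confirming patient eligibility and signing the informed consent".

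**Expected risk.** Section 8.2: "Infection is less likely, occurring in less than 10% of patients, generally following brachytherapy".

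**The concern.** For brachytherapy, protocol exposure begins when the device goes in, not at the first fraction. A complication in those first days can be the reason that no fraction is given. If entry to the safety set requires a fraction, that complication also removes the patient from the set: she leaves numerator and denominator together, and the remaining rate is too low.

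Two decisions use these rates. The per-arm rule in 16.92 suspends accrual. The grade 3 check in 16.43, a difference of at most 10% between techniques, is one of the conditions for the pooled primary analysis. A switched patient adds a second problem. Acute events are analysed regardless of attribution, so without an assignment rule a device event could be tabulated under the external-beam technique that she received later.

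**Working it through.** **1. What starting treatment means.** Section 7.12 uses the idea three times. The first treatment comes after planning, brachytherapy starts some days after placement, and an implanted patient can be stopped before initiation. All three put the start after implantation. Set beside 16.61, 16.62 and 16.92, this gives:

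| Patient | In the 16.61/16.62 set and the 16.92 count? |
|---|---|
| Implanted, device event, goes on to brachytherapy | Yes. The 16.61 window has no lower limit, so the event is not excluded there |
| Implanted, device event, no fraction of any kind | No, on this reading |
| Implanted, switches to photon or proton on study | Yes, but the technique that holds the earlier event is not stated |

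The first row is less secure under 16.3 and 16.92, whose windows are worded as after radiation or after treatment.

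**2. Baseline.** Section 10.4 grades breast infection and seroma at baseline. Footnote 2 of 4.0 permits that grading after implantation, so an early device infection could be entered as a baseline condition. Under 10.1 it would then become an adverse event only on worsening.

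**3. Effect on the 3-in-15 rule (illustration).** There is no plan figure to reproduce. The rule's threshold is 3/15 = 20%. Let p be the true grade 3 or higher rate counted from placement, and f the share of those patients never counted. Both are assumptions. The chance of crossing is P(X ≥ 3) with X binomial, n = 15. The simple version uses rate p(1 − f). If the uncounted patients also leave the denominator, the rate is p(1 − f)/(1 − pf).

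| p | f | p(1 − f) | P(X ≥ 3) | Rate, denominator reduced | P(X ≥ 3) |
|---|---|---|---|---|---|
| 20% | 0 | 20% | 60.2% | 20% | 60.2% |
| 20% | 25% | 15% | 39.6% | 0.15/0.95 = 15.8% | 43.0% |
| 20% | 50% | 10% | 18.4% | 0.10/0.90 = 11.1% | 22.8% |
| 10% | 0 | 10% | 18.4% | 10% | 18.4% |
| 10% | 25% | 7.5% | 9.7% | 0.075/0.975 = 7.7% | 10.3% |
| 10% | 50% | 5% | 3.6% | 0.05/0.95 = 5.3% | 4.1% |

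The 10% rows sit at the upper edge of what 8.2 expects for grade 3 or greater complications (under 10%).

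**4. Effect on the 16.43 check (illustration).** With 40 to 60 patients per technique, one event is worth 1/60 = 1.7 to 1/40 = 2.5 points against the 10-point limit. Assume 40 implanted with 2 other grade 3 patients, and a photon group of 50 with 2 (4.0%).

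- Two uncounted device events: 4/40 = 10.0% against 2/38 = 5.3%. The gap to photon is 6.0 points, or 5.3 − 4.0 = 1.3. The check passes either way.
- Four uncounted device events: 6/40 = 15.0% against 2/36 = 5.6%. The gap is 11.0 points (fails), or 5.6 − 4.0 = 1.6 (passes).

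The second case needs grade 3 device events before any fraction in 4/40 = 10% of implanted women. Section 8.2 expects infection of any grade, at any time, in fewer than 10%. It is an outer case.

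**The case against.** The strongest reply is that the documents never say counting begins at the first fraction. Starting treatment is undefined, and device placement is described within Section 7.0, the protocol treatment section, so placement could be read as treatment. That stands as a possible reading. The wording of 7.12 points the other way, and a suspension rule should not depend on which reading the analyst picks.

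A reader might infer more than the documents support:

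- **That all events before the first fraction are uncounted.** Section 16.61 sets only an upper time limit. Events in women who go on to brachytherapy are not excluded there.
- **That device events are lost to the trial.** Section 10 recording and SAE reporting are not limited to irradiated patients. Section 18.1 provides a form for withdrawal before therapy. Under 16.9 the trial has quarterly and DSMB review, and the team may suspend accrual without the rule being crossed.
- **That infected patients are moved into the photon or proton group by design.** The switch routes in 7.12 rest on dosimetric constraints. Infection and bleeding are not named, and the group for a switched patient is unstated rather than assigned wrongly. The 16.92 relatedness condition also limits what would count against external beam.
- **That the size can be read from the background.** The explantation figure in 1.2 covers one device type at short skin distances and gives no timing.
- **That baseline is defined only by footnote 2.** Section 6.22 lists baseline symptom grading under registration, and 10.1 records worsening as an adverse event. But nothing requires grading before placement.

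A further objection concerns the remedy. Photon and proton patients are generally seen one to six weeks after surgery. An all-cause clock that starts at placement for brachytherapy alone would count early lumpectomy infections and seromas in one technique only. This is right, and it restricts the fix.

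**Conclusion.** The point holds as a gap in the safety set and in attribution. On the natural reading of 7.12, a consented, implanted woman who never receives a fraction is outside the 16.61 and 16.62 analyses and the per-arm suspension count. A switched patient's earlier device events have no assigned technique, and baseline may be graded after implantation.

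The direction is towards understating brachytherapy toxicity; the amount is unknown, because the documents give no rate of device events or removals before the first fraction. Under an assumed 20% true rate with a quarter of events missed, the chance of crossing 3 in 15 falls from 60% to about 40% (43% if the missed patients also leave the denominator). The 16.43 check is unaffected at two missed events in 40 and changes only in the outer case of four. That section does not state its set or window, so any effect on it is conditional. The change is worth making because it protects a safety rule at little cost. It is not evidence that the planned rates are wrong by a known amount.

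**What to change.** - In 16.61, 16.62 and 16.92, include in the brachytherapy safety set every consented patient in whom a device is placed, whether or not a fraction follows.
- From placement to first fraction, count device- or implant-related events only, so that lumpectomy complications are not counted in one technique alone.
- Attribute device-related events to brachytherapy even if the patient later receives photon or proton APBI. Use the same set and attribution for the 16.43 grade 3 check, and state its time window.
- Report device removals before the first fraction, with reason, over all patients implanted.
- For brachytherapy patients, take the 10.4 baseline grading before device placement, and amend footnote 2 of 4.0 to say so.
- Reconcile the one-month acute window in 16.3 with the 90-day window in 16.61.

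The cost is wording in these sections and a device-placement date on an existing form. The reported brachytherapy toxicity rate may rise slightly. Judging whether an early event is device-related or surgical adds an attribution call, which the relatedness condition in 16.92 already requires. No treatment or suspension threshold changes.

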11.3 Cosmesis evaluation and Patient Reported Outcomes

11.31 Digital photographs should be performed according to the schedule outlined in section 4.0 and should include three poses: from the front with hands on hips and both lateral views. Recommended framing should go from the sternal notch to the umbilicus. If possible, patients should be photographed against a solid colored background.

11.32 The Harvard Cosmesis Scale will be used to score cosmesis according to the schedule outlined in section 4.0. The patients will be assessed as one of the following:

- Excellent: treated breast nearly identical to untreated breast
- Good: Treated breast slightly different than untreated (minimal but identifiable effects of the treated breast)

- Fair: Treated breast clearly different from untreated but not seriously distorted (significant radiation effects readily observable)
- Poor: Treated breast seriously distorted (severe sequelae of breast tissue secondary to radiation effects)

A modified version of the Harvard Cosmesis Scale will also be used for patient reported assessment of cosmesis.

11.33 The Breast Cancer Treatment Outcome Scale (BCTOS) is a self-report instrument that has high reliability and validity and will be used for evaluating patient-rated cosmesis according to the schedule outlined in section 4.0.

11.34 Patient-Reported Outcomes Version of the Common Terminology Criteria for Adverse Events (PRO-CTCAE) will be used for patient self-reporting of toxicities in the CTCAE.

11.35 Other Patient Reported Outcome questions (fatigue, pain, arm function etc.) included in the appendix.

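### PRO-CTCAE is collected as patient-reported toxicity, but the analyses that appear to cover it give no count or proportion of women with a severe or worsened score

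*Combined protocol and SAP*

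**What the plan says.** Section 11.34 says that PRO-CTCAE "will be used for patient self-reporting of toxicities in the CTCAE". Section 16.3 repeats this under a heading that joins patient-reported outcomes and quality of life: the instrument "will be used for patient self-reporting of toxicities in the CTCAE, along with other measures of fatigue, pain, and arm function". It is listed there apart from acute and late adverse events.

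No paragraph of 16.6 or 16.7 names PRO-CTCAE. Under the quality-of-life title, 16.63 says: "The QOL measurements will be summarized at each time point as mean" with SD, and as median with minimum and maximum. Changes from baseline follow: "These will be displayed as spaghetti plots", with a paired t-test or Wilcoxon signed-rank test at each time point. Section 16.7 reduces repeated measurements to an area under the curve (AUC), analysed as continuous.

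Other toxicity and patient-reported data are handled differently. For clinician adverse events, 16.61 states: "The maximum grade for each type of acute AE will be recorded for each patient", summarised as frequencies; 16.62 does the same for late events. In 16.64 patient-reported and panel cosmesis "will be summarized with the frequencies of fair or poor cosmesis events at baseline and 3 years", with exact binomial intervals.

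**The concern.** The protocol states its toxicity expectations as rates. Section 8.2 says that "any grade 3 or greater complications including pain are uncommon after ABPI, and are expected to occur in <10% of patients", and 16.62 cites earlier grade 3 or 4 rates of at most 10%. A patient-reported instrument built around toxicity would naturally yield a rate as well. As written, the trial would report how far the average score moved, but not how many women rated a symptom severe or worse than before radiation.

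At stake are the goal on quality of life and other patient-reported outcomes (the second item numbered 2.23) and the patient-reported part of the technique comparison (the first item numbered 2.24).

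**Working it through.** **Inputs.** n = 153 is from 16.41. It can be reproduced from 16.42 (one-sided 95%, 10% assumed, 4 points to the bound): 1.645² × 0.10 × 0.90 / 0.04² = 152.19, rounded up to 153. The plan gives no figure for PRO-CTCAE. Assumed here: ordered scores 0, 1, 2, 3 with 3 = severe, and complete data.

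**Step 1: the follow-up summary does not fix the severe count.** Take one woman out of score 0 and three out of score 2, and put three at score 1 and one at score 3. This leaves n, the sum and the sum of squares unchanged. Doing it ten times turns case A into case B.

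| Women at score | 0 | 1 | 2 | 3 | Sum | Sum of squares |
|---|---|---|---|---|---|---|
| A | 100 | 20 | 30 | 3 | 20+60+9 = 89 | 20+120+27 = 167 |
| B | 90 | 50 | 0 | 13 | 50+39 = 89 | 50+117 = 167 |

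Mean = 89/153 = 0.58. SD = √[(167 − 89²/153)/152] = 0.87. Median 0 and range 0 to 3 in both.

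**Step 2: nor do the mean change and t-test.** Let 31 women go from 1 to 0 and all others start at 0. Baseline is 0.20 ± 0.40, median 0, range 0 to 1. For change, the sum is 89 − 31 = 58 and the sum of squares is 167 + 31 = 198. Mean change is 58/153 = 0.38, SD = √[(198 − 58²/153)/152] = 1.08, median 0, range −1 to 3, t = 4.36, p = 0.00002 in both.

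**Step 3: what differs.** Severe: 3/153 = 2.0% (exact 95% CI 0.4% to 5.6%) against 13/153 = 8.5% (4.6% to 14.1%). Worsened: 20+30+3 = 53 women (34.6%) against 50+13 = 63 (41.2%). Average worsening is detected in both cases; how many women are severe is not shown.

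The signed-rank test does not match: p = 0.000006 (A) and 0.00008 (B). With 61 women resolving instead of 31, the t-test gives p = 0.064 in both, but the signed-rank test gives 0.021 (A) and 0.21 (B). The spaghetti plots would differ too, since A has 30 women at score 2 and B has none.

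**Step 4: a five-level scale.** With scores 0 to 4 and severe = 3 or 4, counts (125, 0, 18, 0, 10) and (128, 0, 0, 24, 1) share sum 76 and sum of squares 232, so mean 0.50, SD 1.13, median 0, range 0 to 4. Severe: 10/153 = 6.5% against 25/153 = 16.3%. With two or three levels the argument fails, because n, mean and SD then determine the counts.

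**Step 5: AUC.** With annual visits and the trapezoid rule, a 3 at year 2 only gives ½ × 3 × 2 = 3.0. A 1 at years 2, 3 and 4 gives 0.5 + 1 + 1 + 0.5 = 3.0. Only the first woman ever had a severe score.

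**The case against.** **The assignment to 16.63 is an inference.** Nothing says outright that PRO-CTCAE is analysed there. The adverse-event table in 10.4 lists BCTOS, a self-report scale, beside CTCAE for breast edema, so one could argue that the maximum-grade tables of 16.61 and 16.62 admit patient reports. The inference remains the better reading: 10.2 ties adverse-event grading to CTCAE version 4.0, the 10.4 table does not list PRO-CTCAE, and 16.3 defines the patient-reported and quality-of-life endpoint by naming it. Section 16.7 does allow chi-square or Fisher tests for categorical variables, but it defines no category for any patient-reported item.

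**Cases A and B are not identical under every planned output.** This stands. The signed-rank p-values and the plots differ. Neither supplies a count: a p-value is not a rate, and about 150 overlapping lines on a few ordered levels cannot be counted reliably.

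**A severe patient score is not clinician grade 3.** This stands, so a patient-reported rate would give context for the 10% figures, not test them. Clinician grading at each evaluation continues regardless.

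**The proportion could be tabulated later.** It could, but the cut-point would then be chosen with the data in view.

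**A stronger reading to avoid.** A reader might infer that the planned tests would hide a severe minority, because surgical symptoms resolve in other women after a postoperative baseline. That can happen but depends on assumptions outside the documents. In simulation with 10% newly severe (0 to 3) and 20% resolving (1 to 0), the t-test declares worsening 19% of the time if nobody worsens mildly (0 to 1), but 64%, 94% and over 99% if 10%, 20% or 30% do. Section 8.2 expects mild effects: "Mild swelling of the breast or mild breast pain are also likely side effects of treatment". Baselines taken before surgery are not exposed to this at all.

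**Conclusion.** The point holds as an inexpensive improvement to a secondary analysis. On the best-supported reading, the plan produces no rate of severe or worsened patient-reported toxicity, although it produces such rates for clinician-graded events and patient-reported cosmesis. At n = 153 the tabulated summaries and the paired t-test can be the same with 2.0% or 8.5% of women severe. This rests on items having four or more levels, on 3 being the severe score in the four-level example, and on complete data.

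The documents do not support saying that PRO-CTCAE certainly lacks an applicable analysis, or that toxicity would go undetected. The data are collected, and average worsening can be detected. The primary endpoint and its 14% rule, the clinician CTCAE analyses and the stopping rules in 16.92 are unaffected.

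**What to change.** Name PRO-CTCAE in 16.6 and give it its own paragraph:

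- For each item, in an acute and a late window, report the number and percentage, with exact 95% CI, of women whose maximum post-baseline score is severe and above their own baseline. The denominator is women with a baseline score and at least one score in that window.
- Add a table of maximum score by baseline score, which also shows milder worsening.
- Fix the severe cut-point for each item before analysis.
- Use the 90-day cut of 16.61 and 16.62, and bring the one-month definition of acute in 16.3 into line with it. Assign scores by actual assessment date: section 4.0 sets the 12-week visit at ±8 weeks (84 ± 56 days, so day 28 to day 140), which straddles day 90.
- Under 16.7, any comparison of these proportions between techniques is exploratory and unadjusted, using the chi-square or Fisher test already listed, with 40 to 60 women per technique.
- Keep the 16.63 means, plots and paired tests as a supplement.

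The cost is SAP wording and a few tables from data already collected, with no change to design or sample size. A proportion is less sensitive than a mean to a small uniform shift; the retained means cover that.
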